#### *Exploratory outcomes*

1. Recall of acute pain at 12 and 24 hours after CD. Asked 12 months after CD.
2. Percentage of patients experiencing pain with an NRS > 3 at 1, 2, 3, and 12 months, as well as 2, 3, 4, and 5 years after CD.
3. Association between severe acute pain (NRS > 6) during the first 24 hours and the occurrence of persistent pain at 6 and 12 months after CD.
4. Prevalence of chronic pain before pregnancy.
5. Prevalence of chronic pain before pregnancy and its association with the development of persistent pain at 6 and 12 months, and 2, 3, 4, 5 years after CD.
6. Association between uterine exteriorization versus in situ repair in CD and the occurrence of persistent pain at 6 and 12 months, as well as 2, 3, 4, and 5 years after CD.

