## Background

In Denmark, around 12,700 patients undergo cesarean delivery (CD) annually, constituting approximately 20% of all childbirths in the country (Danish Birth Registry 2023). Worldwide, the number is increasing yearly with more than 20 million CDs performed annually (Betran et al. 2021).

Postoperative pain after CD is typically moderate to severe in intensity and still constitutes a significant challenge, balancing effective pain relief and potential side effects ([name], [name] and [name] 2023; Lindelof et al. 2022; Roofthooft et al. 2021). Correlations between moderate to severe acute pain and the development of persistent pain after CD is still unclear (Eisenach et al. 2008; Nikolajsen et al. 2004; Sun and Pan 2019; Yimer and Woldie 2019).

Persistent pain is observed after various surgical procedures, posing a challenge for many patients (Kehlet, Jensen, and Woolf 2006). The reported incidence of persistent pain after CD varies considerably among studies; in a review of persistent pain after CD (Sun and Pan 2019) 11-27% of patients reported pain after six months. Four Danish studies have addressed acute pain following CD in the Danish population ([name],

[name], and [name] 2023; Hansen et al. 2019; Lindelof et al. 2022; Nikolajsen et al. 2004). One of these studies has also examined the occurrence of persistent pain (Nikolajsen et al. 2004); in a single-center study including 220 patients with a mean follow-up time of 10.2 months (range 6-17.6). Nikolajsen et al. concluded that 5.9% of the patients experienced pain from the cesarean scar area, daily or almost daily. To our knowledge, no studies have prospectively explored the potential effects of postoperative pain on functional outcomes and the ability to care for the infant beyond the early postoperative period.

Both pre-, intra-, and postoperative factors have been associated with an increased risk of persistent pain after surgery (Kehlet, Jensen, and Woolf 2006; Sun and Pan 2019). Current approaches to persistent pain prevention aim to use surgical techniques that avoid nerve damage, reduce tissue injury, optimize multimodal analgesia, and reduce acute postoperative pain (Kehlet, Jensen, and Woolf 2006; Sun and Pan 2019, Tan et al. 2022). The current predominance of evidence emphasizes an association between the severity of acute pain after surgery and the development of persistent pain (Yimer and Woldie 2019).

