## Objective

This study aims to describe the occurrence of persistent postoperative pain in a cohort of Danish patients who have undergone elective CD. The outcomes are focused on pain levels, the impact of pain on physical function, and neuropathic pain characteristics in the months and years following the CD. The study also aims to explore the relationship between persistent and acute pain.

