## Development and validation of questions

PROMs are collected through SMS-based questionnaires. The questionnaires were developed with inspiration from studies on chronic pain (Kehlet 2006) and studies specific for the CD population (Eisenach et al. 2008; Nikolajsen et al. 2004; Sun and Pan 2019; Yimer and Woldie 2019). The Numeric Rating Scale (NRS) 0-10 was employed for pain assessment (Eisenach et al. 2008) and a 1-5/6 scale was utilized for PROMs related to function.

As part of the process of developing the questionnaires, we sought input from patients, anesthetists, and obstetricians to identify key areas relevant to representing recovery and pain in the months and years after CD, and we conducted five structured interviews with CD patients 3–6 months post-surgery. Subsequently, questions were developed and tested using standardized survey design methods (Duffett et al. 2011; Eysenbach 2004). The questionnaires underwent initial testing on professionals and the same five CD patients who had participated in the interviews. Adjustments were made based on this feedback. The questionnaires were then re-tested on both professionals and the five CD patients, with no further adjustments needed. Following this, the questionnaires were programmed into the web-based REDCap database (Research Electronic Data Capture) (Harris et al. 2009) and optimized for presentation on smartphone screens. Finally, the questionnaires were set-up to be sent out as an SMS via an external server (Sure-SMS, Denmark) with links to the questionnaires in REDCap. The questionnaires sent at various time points consist of 23 short questions, that can be answered on the phone in less than 5 minutes.

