### *Data Processing and statistics*

All data will be handled in the REDCap database. Descriptive statistics will be used to analyze data. Continuous data will be summarized as median (interquartile range) or mean (standard deviation) if the data is normally distributed, and categorical data as frequency (percentage). Subgroup analyses are planned for: Severe acute pain and the association of persistent pain; the association between uterine exteriorization versus in situ repair and the occurrence of persistent pain; as well as the prevalence of chronic pain before pregnancy and its association with the development of persistent pain. We will try to minimize missing data as much as possible by sending questionnaires directly to the participants mobile phones and sending reminders. The amount of missing data will be accounted for when describing data. The sample size is determined by convenience, with an expected participation rate of approximately half of the 700 patients from the initial cohort study agreeing to continue with the questionnaires on persistent pain. We analyze the data when the last of the included patients have completed the 12-month questionnaire and again after every year.

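### Exploratory outcome 3 takes acute pain only as NRS above 6 or not, which pools moderate with no or mild acute pain and, if risk rises steadily, loses roughly a third of the information

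*Protocol*

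**What the plan says.** Protocol, Exploratory outcomes, item 3, defines the analysis as "Association between severe acute pain (NRS > 6) during the first 24 hours and the occurrence of persistent pain at 6 and 12 months". Data Processing and statistics repeats it with the same exposure: "Subgroup analyses are planned for: Severe acute pain and the association of persistent pain". Neither place names a graded, ordinal or numeric version of acute pain.

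Three other sections bear on the choice:

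- The Background states that "Correlations between moderate to severe acute pain and the development of persistent pain after CD is still unclear", describes the existing evidence as "an association between the severity of acute pain after surgery and the development of persistent pain", and says that "Postoperative pain after CD is typically moderate to severe in intensity".
- The Objective states: "The study also aims to explore the relationship between persistent and acute pain".
- Development and validation of questions says that "The Numeric Rating Scale (NRS) 0-10 was employed for pain assessment".

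Item 3 gives no threshold for persistent pain. The primary outcome uses NRS > 3 at 6 months, and exploratory outcome 2 applies the same threshold at other times, including 12 months. That threshold is assumed here.

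**The concern.** With one cut at NRS > 6, the comparison group is everyone with acute NRS 0-6. Moderate scores (4-6) are merged with no or mild pain (0-3). The Background's question includes moderate pain and is about severity, so the contrast answers a narrower question than the one that motivates it. If pain is typically moderate to severe, the moderate group is probably large, and all of it except the severe part falls in the reference group.

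If the risk of persistent pain climbs with each step of acute pain, the moderate scorers raise the reference risk and shrink the contrast. The gradation within each side of the cut is also discarded. In a cohort of this size, with few cases at 6 months, that makes a real relationship harder to see on a stated aim of the study.

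**Working it through.** **What the protocol supplies.** It gives no power, effect size, acute NRS distribution or information figure for this association, so there is no stated figure to reproduce. The sample is by convenience: 0.5 × 700 = 350, consistent with the target of at least 300.

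**Check 1: formula for cutting a normal predictor with a linear effect.** Let p be the share above the cut and z the normal quantile at 1 − p. Then information retained = φ(z)² / [p(1 − p)], and loss = 1 − retained.

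| Share above NRS 6 | Retained | Loss |
|---|---|---|
| 10% | 0.342 | 66% |
| 13.3% | 0.40 | 60% |
| 20% | 0.490 | 51% |
| 30% | 0.576 | 42% |
| 40% | 0.622 | 38% |
| 50% | 0.637 | 36% |

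For p = 30%: z = 0.524, φ(z) = 0.348, and 0.348² / 0.21 = 0.576.

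An 11-level score (rounded normal, mean 3-7, SD 1.5-3) gives losses from 29% to 93%. Moderate scores make up 36-97% of the reference group. With mean 5 and SD 2, 23% exceed 6, the loss is 47%, and moderate scores are 71% of the reference group.

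**Check 2: a model with binary persistent pain.** Assumptions, none from the protocol: 80% response, so 350 × 0.80 = 280 women; acute NRS a rounded normal with SD 2.3 and 30% above 6; 8% with NRS > 3 at 6 months; latent correlation 0.20.

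- Expected cases: 280 × 0.08 ≈ 22 (17 to 31 if the prevalence is 6-11%).
- Risk by acute band: 4.5% (0-3), 7.3% (4-6), 11.6% (above 6).
- Moderate scores are 69% of the reference group, so the reference risk is 0.31 × 4.5 + 0.69 × 7.3 = 6.4%.
- The planned contrast is 11.6% against 6.4%, a ratio of 1.8. Severe against no or mild pain is 11.6% against 4.5%, a ratio of 2.6.

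For n women with mean risk Y, the noncentrality of the test on exposure X is n · Cov(X, risk)² / [Var(X) · Y(1 − Y)], and the loss is 1 minus the ratio of the cut to the numeric version. Simulation puts this at about 31-36% for 20-40% of women above NRS 6. Evaluating the formula numerically gives about 2.2 for the cut and 3.3 for the numeric score in the central setting, a loss of 32%. It gives 29-39% over prevalences of 6-11% and correlations of 0.20 and 0.25. This is below the first check because the modelled risk climbs faster at the top of the scale, which favours a high cut.

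**Check 3: which cut costs what.** Simulated power at two-sided 5% in the central setting is 34% with both variables cut, 43% with acute NRS numeric and the outcome still NRS > 3, and 70% with both scores kept on 0-10. Noncentrality is roughly (z for the power + 1.96)², which gives 2.39, 3.18 and 6.17.

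- Acute cut alone: 1 − 2.39/3.18 = 25%, a coarser figure because it comes from rounded powers.
- Outcome cut alone: 1 − 3.18/6.17 = 48%.
- Both cuts: 1 − 2.39/6.17 = 61%.

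**The case against.** The case for leaving the text alone has several parts. Whether severe acute pain predicts persistence is a legitimate and clinically readable question, and the two places that define the analysis agree with each other. The Objective does not promise a dose-response analysis. The item is exploratory, in a descriptive cohort with no test or power claimed. A statistical analysis plan that is not shown could add a graded analysis. If risk steps up only at severe pain, the cut costs nothing.

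Most of this stands. It shows that there is no contradiction in the protocol and that the priority is modest. It does not remove the point: the cut is written into the outcome definition rather than left open, it is the only acute exposure named, and it fits poorly with a rationale built on severity. A graded analysis with banded risks would also reveal a step at 6 if there is one.

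Two stronger readings are not supported. A reader might infer that the acute cut loses about 60% of the information. On the exposure side alone, the formula gives that only if about 13% of women exceed NRS 6, a share the protocol does not state. The similar 61% in the third check arises only when persistent pain is also moved off NRS > 3, and most of it comes from that second change. Replacing the occurrence of persistent pain with the whole 0-10 score asks a different question. A reader might also take the reference group to be pain-free, but it is everyone with NRS 0-6.

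**Conclusion.** The point holds as a modest improvement. The exposure in exploratory outcome 3 merges moderate with no or mild acute pain and discards the 0-10 gradation, although the Background and Objective frame the question around severity.

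If risk rises steadily, the acute cut costs roughly a third of the information: about 31-36% in the simulated model for 20-40% above NRS 6, 36-66% by the normal-predictor formula for 10-50% above 6, and nil if risk is a true step at 6. In the central setting this is power of 34% against 43%, so even the better analysis has limited power.

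The acute distribution, response rate, prevalence and correlation are all assumptions. That the persistent-pain threshold is NRS > 3, and that the parent cohort holds usable 0-10 acute scores, is inferred from this protocol; the parent protocol is not shown.

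**What to change.** In exploratory outcome 3, and in the matching sentence of Data Processing and statistics:

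- Make acute NRS (0-10, first 24 hours, as recorded in the parent cohort) a numeric exposure in a logistic regression of NRS > 3 at 6 and at 12 months. Report the odds ratio per point with its confidence interval.
- Show observed risks for acute 0-3, 4-6 and 7-10.
- Keep the NRS > 6 contrast as a supplementary display.
- An ordinal model of the persistent NRS may be added as a sensitivity analysis only, since it addresses a different outcome.

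The cost is wording and slightly more analysis. No new patients are needed, and no new data provided that the parent cohort holds the acute scores as numbers. The downside is a linearity assumption, which the banded risks let readers check roughly. Those bands are for description, not testing: under the central assumptions the 0-3 band holds about 280 × 0.70 × 0.31 ≈ 61 women and 61 × 0.045 ≈ 3 cases.

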## Development and validation of questions

PROMs are collected through SMS-based questionnaires. The questionnaires were developed with inspiration from studies on chronic pain (Kehlet 2006) and studies specific for the CD population (Eisenach et al. 2008; Nikolajsen et al. 2004; Sun and Pan 2019; Yimer and Woldie 2019). The Numeric Rating Scale (NRS) 0-10 was employed for pain assessment (Eisenach et al. 2008) and a 1-5/6 scale was utilized for PROMs related to function.

As part of the process of developing the questionnaires, we sought input from patients, anesthetists, and obstetricians to identify key areas relevant to representing recovery and pain in the months and years after CD, and we conducted five structured interviews with CD patients 3–6 months post-surgery. Subsequently, questions were developed and tested using standardized survey design methods (Duffett et al. 2011; Eysenbach 2004). The questionnaires underwent initial testing on professionals and the same five CD patients who had participated in the interviews. Adjustments were made based on this feedback. The questionnaires were then re-tested on both professionals and the five CD patients, with no further adjustments needed. Following this, the questionnaires were programmed into the web-based REDCap database (Research Electronic Data Capture) (Harris et al. 2009) and optimized for presentation on smartphone screens. Finally, the questionnaires were set-up to be sent out as an SMS via an external server (Sure-SMS, Denmark) with links to the questionnaires in REDCap. The questionnaires sent at various time points consist of 23 short questions, that can be answered on the phone in less than 5 minutes.

## Data collection

The questionnaires are sent at fixed time intervals: at 5 weeks, 2 months, 3 months, 6 months, and 12 months, and thereafter every 6 months until 5 years after CD. Reminders are sent the day after the initial questionnaire in case of no response. All questionnaire data are entered directly into the closed and secure system REDCap. Data from journal entries are also entered into REDCap. At all hospitals, a data manager can retrieve data for the patients included in the project. The primary investigator holds the overall responsibility for the data.

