## Number of participants

We aim to include at least 300 patients from all 5 regions in Denmark. The final number of participants will depend on the cohort size from the ongoing study ([name] et al. 2023).

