### *Primary outcome*

The percentage of patients reporting pain equivalent to an NRS score > 3 after 6 months

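### A single next-day reminder time applies to every round, including the 6-month round that alone supplies the primary outcome; later reminders and a stated response window would be a cheap improvement

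*Protocol*

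**What the plan says.** Under Data collection, the protocol sets the contact schedule: "The questionnaires are sent at fixed time intervals: at 5 weeks, 2 months, 3 months, 6 months, and 12 months", followed by half-yearly rounds. For those who do not answer, the rule is "Reminders are sent the day after the initial questionnaire in case of no response". No later reminder, second contact route, response window or closing time for the link is given, and no round is treated differently from the others.

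The primary outcome is "The percentage of patients reporting pain equivalent to an NRS score > 3 after 6 months", so it rests on the 6-month round alone.

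Under Data Processing and statistics, the measures against missing data are SMS delivery and reminders: "We will try to minimize missing data as much as possible by sending questionnaires directly to the participants mobile phones and sending reminders". For the analysis the text adds "The amount of missing data will be accounted for when describing data". On size, "The sample size is determined by convenience", with an "expected participation rate of approximately half of the 700 patients from the initial cohort study". Number of participants says "We aim to include at least 300 patients from all 5 regions in Denmark". No expected response at 6 months and no allowance for non-response are stated.

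Under Informed consent, participants are asked within the 12-month questionnaire, and again at 2, 3 and 4 years, whether they wish to continue.

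**The concern.** A participant who overlooks the 6-month SMS and the next-day reminder gets no further prompt for that round under the stated rule. No other round can replace it in the primary percentage. The next questionnaire comes six months later, so a longer chase would not run into another round.

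What is at stake is mainly bias. Whether a participant answers may depend on whether she has pain: those with pain may find the questions more relevant, or may be less able to reply. The protocol gives no basis for choosing between these, so the direction is open. In the analysis it commits only to accounting for the amount missing. Prevention at collection is therefore the main protection it states.

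The 12-month round matters for a second reason. A participant who does not open that questionnaire does not see the question about continuing, and no other way of asking it is described. Non-response there can therefore also cost later follow-up.

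**Working it through.** **The plan's own figures.** Half of 700 is 0.5 × 700 = 350, which is consistent with the floor of 300. The sample is one of convenience, so there is no power or precision calculation to reproduce. The number lost at 6 months cannot be computed because no response rate is given. All response rates, recovery rates and rate ratios below are assumptions.

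**Illustration A: 350 enrolled, 10% with NRS > 3 among responders.**

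- Precision: half-width = 1.96 × √(p(1 − p)/n).
  - 75% response, n = 262: 1.96 × √(0.10 × 0.90/262) = 3.6 points.
  - 90% response, n = 315: 1.96 × √(0.10 × 0.90/315) = 3.3 points.
- Bias at 75% response: true percentage = r × p + (1 − r) × k × p, where r is the response and k the ratio of the non-responders' rate to the responders' rate.
  - k = 2: 0.75 × 10% + 0.25 × 20% = 12.5%. The reported 10% is 2.5 points too low.
  - k = 0.5: 0.75 × 10% + 0.25 × 5% = 8.75%. The reported 10% is 1.25 points too high.
- If later reminders recovered half of the non-responders at random and k = 2, response would be 0.75 + 0.125 = 0.875. The reported value would be (0.075 + 0.125 × 0.20)/0.875 = 11.4% against a true 12.5%, so the bias falls from −2.5 to about −1.1 points.
- Extreme bounds, with none or all of the non-responders above NRS 3:
  - 75% response: 0.75 × 10% = 7.5% to 7.5% + 25% = 32.5%.
  - 90% response: 9% to 19%.

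**Illustration B: 300 enrolled, 11% among responders.** The 11% is the lower end of the 11–27% range for pain at six months quoted in Background. It is used only to set a scale.

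| Response | Answers | Missing | Half-width (points) | Bias, k = 2 | Bias, k = 2, half recovered | Bias, k = 0.5 | Bias, k = 0.5, half recovered |
|---|---|---|---|---|---|---|---|
| 90% | 270 | 30 | 3.7 | −1.1 | −0.52 | +0.55 | +0.26 |
| 80% | 240 | 60 | 4.0 | −2.2 | −0.98 | +1.1 | +0.49 |
| 70% | 210 | 90 | 4.2 | −3.3 | −1.36 | +1.65 | +0.68 |
| 60% | 180 | 120 | 4.6 | −4.4 | −1.65 | +2.2 | +0.82 |

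At full response the half-width would be 3.5 points. Precision therefore changes by about one point across the whole range. Possible bias can reach the size of the half-width itself, and recovering half of the non-responders cuts it by somewhat more than half.

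**The case against.** A reader might infer that answers are accepted for only about two days and that recoverable participants are in fact lost. The documents do not support this. The protocol says when reminders go out; it states no response window, no link expiry and no exclusion of late answers. An SMS stays on the phone, and a participant may reply later unprompted. That nobody is chased after the next day also rests on the protocol's silence: the word for reminders is plural, although only one time is given. Participants can be lost; the text does not show that they are.

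A reader might also see a contradiction with the stated aim of keeping missing data low. There is none. That sentence names SMS delivery and reminders as its means, and the schedule provides both. How many reminders to send is a judgement of yield against burden.

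The cohort is favourable to this route. Participants join by agreeing inside an earlier questionnaire, must have a smartphone that can open the link, and face a form of under five minutes. The reference list includes a feasibility study of SMS questionnaires after cesarean section, so the sponsor may hold response data not shown here. The assumed 75% could be too pessimistic, and nothing in the document shows that extra messages would raise response to 90%.

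Finally, the 32.5% upper bound requires every non-responder to be above NRS 3. It is a logical limit, not a plausible value, and should not be read as the size of the problem.

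These objections remove any claim of error and any claim of a known loss. They leave standing that one reminder time serves a round on which the primary outcome wholly depends, and that a later prompt with a stated window would reduce avoidable non-response at little cost.

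**Conclusion.** The point holds as a cheap improvement to a stated data-collection rule. It is not an error or contradiction. The contact schedule is fixed in the protocol itself, so this is not a matter left to a statistical analysis plan.

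The size is unknown. Under the illustrative assumptions (10% among responders, 75% response, non-responders at twice that rate) the primary percentage would be about 2.5 points too low. If non-responders had half the rate, it would be about 1.25 points too high. The case rests on limiting this possible bias; the gain in precision, from 3.6 to 3.3 points, is too small to justify the change alone. The benefit also depends on later reminders reaching people who would not otherwise have answered, for which the protocol offers no figure.

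**What to change.** In Data collection, at least for the 6- and 12-month rounds:

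- Keep the next-day reminder and add one or two later automated SMS reminders to those who have not answered, for example around day 4 and day 10.
- State a response window, for example 3 weeks, within which an answer counts for that round, and store the completion date.
- If the last reminder carries a shortened form, use the same NRS item and recall period as the primary outcome. The two NRS items listed under Secondary outcomes refer to the last 24 hours, so a question about pain at this moment would mix two measures in one percentage.

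The days and the window are examples; other workable values would serve. The questionnaires already run through REDCap and an SMS server, so this is a change of schedule with no added staff or visits. The costs are up to two extra messages to non-responders at those rounds and answers spread over up to 3 weeks. Limiting the change to these two rounds keeps the burden small in a voluntary cohort that is asked each year whether to continue. Rounds already closed cannot be recovered.
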